2.3 Perioperative management of children, analgesia and anesthesia

The induction of general anesthesia will be obtained in all children through bolus doses of 1 mg/kg over 20 s of intravenous propofol, followed by similar bolus doses of propofol until the patient will be anesthetized, and anesthesia was maintained with inhaled sevoflurane.

Children will be considered anesthetized when they are asleep and unarousable, and the eyelash reflex disappear. Thereafter, anesthesia will be maintained with inhaled sevoflurane.

At the end of the surgery, after returning to the ward, all patients will be assessed for postoperative pain using the Face, Legs, Activity, Cry, and Consolability (FLACC) scale. If FLACC score is greater than 3, the analgesic drug paracetamol will be administered at the dose of 15 mg/kg, every six hours at most. Clinical and research personnel will be unaware of the group assignments until the completion of data analysis. The number of doses of paracetamol administered to children of both treatment conditions within 48 hours after surgery, even if discharged, will be recorded.

2.4 Melatonin, 4-Hydroxynonenal, and SIRT1 Measurements

Samples of 0.2 mL of plasma will be collected at T0 (pre-hospitalization, 1 day before surgery), T1 (after anesthesia, immediately before surgery) and T2 (at 1 h after the end of the surgery and awakening after anesthesia), and biochemical analyses will be performed.

Melatonin plasma levels will be assessed at each experimental time point (T0, T1, T2) using a competitive enzyme-linked immunosorbent assay (cELISA) kit from Antibodies.com (A87093) according to the manufacturer's instructions. T1 and T2 plasma samples from Mel treated children suspected of containing concentrations higher than the highest standard (500 pg/mL) will be diluted 1:100 (v/v) with sample diluent prior to analysis. Color development will be monitored at 450 nm in a Thermo Scientific (MultiSkan FC) microplate reader, and a standard curve (range 7.813-500 pg/mL) will be generated using a four-parameter logistic (4-PL) curve fit.

4-Hydroxynonenal (4-HNE) as a marker of lipid peroxidation will be measured to evaluate OS by using a cELISA kit from Antibodies.com (A86962). Plasma concentrations will be calculated by reading the absorbance at 450 nm and referring to the standard curve (range 31.25-2000 pg/mL). SIRT1 will be quantified using an ELISA kit from Invitrogen (EH427RB). Plasma samples will be diluted 1:2 as indicated by the Manufacturer before analysis. SIRT1 concentrations will be calculated by absorbance reading at 450 nm and referring to the standard curve (range 1.23-300 ng/mL).

2.5 Quantitative real-time PCR for mature microRNAs analysis

MicroRNA analyses will be performed based on the quali-quantitative plasma sample available (N=3 at each time point, T0, T1, and T2). MicroRNAs (miR-34 and miR-124a) will be isolated from plasma using the Norgen total RNA isolation kit¹. The Plasma microRNAs and spike-in cel-miR-39 expressions will be evaluated using the TaqMan miRNA assay. The TaqMan miRNA reverse transcription kit will be used to reverse transcribe miRNAs. Subsequently, RT-qPCR will performe in 20 µL of PCR mix containing 1 µL of 20× TaqMan miRNA assay, which contained PCR primers and probes (5'-FAM), 10 µL of 2×TaqMan Universal PCR Master Mix No Amp Erase UNG and 5 µL of reverse-transcribed product. The reaction will be first incubated at 95 °C for 10 min followed by 40 cycles at 95 °C for 15 s and at 60 °C for 1 min. The quantitative real-time PCR (RT-qPCR) will be performed on a ABIPRISM 7500 Real Time PCR System. Data will be analyzed by a 7500-system software (1 1.4.0) with the automatic comparative threshold (Ct) setting for adapting baseline. Detection thresholds were set at 35 Ct. The relative amounts of miR-34 and miR-124a will be calculated using the Ct method: $\Delta Ct = Ct (miR-34/miR-124a) - Ct (reference miRNA); 2^{-\Delta Ct}$.

2.6 Data analysis

Data will be expressed as mean (standard error, SE) or median (interquartile range, Q1-Q3) as appropriate. Differences between T0, T1, and T2 will be analyzed by repeated measures ANOVA followed by Tukey's multiple comparison test for melatonin, 4-HNE, miR34 and miR124a plasma levels, while by Friedman test followed by Dunn's test in the case of SIRT1 levels. At each experimental time point, comparisons between the Control and Mel treated children will be performed using Student's t-test for unpaired data or Mann-Whitney U test as appropriate. Linear regression analyses will also be performed to examine correlations between variables (Pearson correlation). All data with P < 0.05 will be considered statistically significant. GraphPad Prism 6.0 (GraphPad Software, Inc., San Diego, CA, USA) will be used for statistical analysis.

References

Fischer S, *et al.* Role of anxiety in young children's pain memory development after surgery. *Pain* 160, 965-972 (2019).

Perrone S, *et al.* Oxidative Stress as a Physiological Pain Response in Full-Term Newborns. *Oxid Med Cell Longev* 2017, 3759287 (2017).

Marseglia L, *et al.* Antioxidant Effect of Melatonin in Preterm Newborns. *Oxid Med Cell Longev* 2021, 6308255 (2021).

Perrone S, *et al.* Melatonin in Newborn Infants Undergoing Surgery: A Pilot Study on Its Effects on Postoperative Oxidative Stress. *Antioxidants (Basel)* 12, (2023).

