Analgesic and Antioxidant Effects of Melatonin in Pediatric Surgery

Protocol Version

v. 1.0

Date:

September 15th 2020

1. Introduction

Pediatric patients undergoing surgery are at significant risk for experiencing postoperative pain. Studies have shown a high prevalence of pain and behavioral problems that can persist for several weeks after surgery. The memory of perioperative pain in children can be distressing and have lasting consequences. Children who develop negatively biased pain memories are more likely to experience poorer pain outcomes in the future. Research has shown that children with such memories experience increased postoperative pain several days after surgery. In addition, inadequate management of acute postoperative pain may contribute to problems such as postoperative bleeding and impaired recovery. These findings underscore the importance of effectively managing postoperative pain to potentially prevent the formation of negatively biased pain memories in young children. In addition, acute pain activates the nociceptive system and triggers a stress response involving the sympathetic nervous system and the hypothalamic-pituitary-adrenal axis. This cascade leads to cerebral, autonomic, and hormonal responses and induces changes in several biochemical processes. Pain has been shown to be associated with oxidative stress (OS) in response to tissue injury, inflammation, and cytokine production.

Melatonin, a neurohormone produced by the pineal gland, plays a role in the nociceptive modulation of various types of pain. Melatonin has anti-inflammatory and antioxidant properties. Early oral

administration of melatonin in infancy has been shown to significantly reduce plasma levels of OS biomarkers such as total hydroperoxides and advanced oxidation protein products.

High levels of these OS biomarkers have been observed in neonates with high pain scores, demonstrating a strong relationship between pain and OS. Melatonin shows a potential role in protecting neonates undergoing surgery from the deleterious effects of OS. After administration of exogenous melatonin, a significant reduction in lipid and protein peroxidation in the postoperative period has been reported in neonates. Recently, Song et al. reported that sirtuin 1 (SIRT1) also plays a critical role in the pathogenesis of pain, showing analgesic effects in chronic pain conditions such as neuropathic and inflammatory pain.

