Several studies have shown that lipid peroxidation is involved in different types of pain, such as cancer pain, fibromyalgia, and neuropathic pain. 4-HNE plasma levels are good indices of free radical damage on lipids. Lipid damage from free radical exposure leads to lipid hydroperoxide generation from lipids and to carbonyl formation and protein hydroperoxide generation from proteins. Lipid peroxidation reaction leads to increased endogenous production of reactive aldehydes and their derivatives, such as malondialdehyde and 4-HNE²⁰. Malondialdehyde is the most mutagenic by-product of lipid peroxidation, while 4-HNE is the most toxic. 4-HNE is often used as a marker of OS and has been implicated in the pathogenesis of cancer, neurodegenerative diseases, diabetes, and other diseases. 4-HNE is involved in many pathophysiological signaling pathways SIRT1, acting as a NAD⁺-dependent deacetylase, plays a crucial role in critical cellular functions such as energy metabolism, genomic stability, inflammation, and immune response. Due to its multifunctional role, SIRT1 has been considered a promising target for therapies aimed at treating various conditions, including metabolic disorders and age-related diseases. Decreased SIRT1 levels have been observed in the spinal cord of various pathological pain models, in which SIRT1 activation helped alleviate chronic pain by regulating inflammation, oxidative stress, and mitochondrial dysfunction.

Recent animal studies have demonstrated that miRNAs are involved in pain processing pathways. Ikuma et al. found the increased extracellular release of microRNAs from dorsal root ganglion cells in a rat model of neuropathic pain.

In this prospective, randomized, double-blind pilot study, we test the hypothesis that melatonin, administered as premedication before induction of anesthesia, reduces OS and postoperative pain involving the sirtuin pathway in children undergoing minor abdominal surgery.

The relationship between pain and 4-HNE, between 4-HNE and melatonin levels, and between microRNAs and SIRT1 levels will be investigated.

2. Methods

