2.1 Recruitment and Randomization

The trial is approved by the local Ethics Committee (LocalNo.125222022) according to the Helsinki Declaration of 1964. Patients' legal guardians will provide written informed consent.

Fifteen Children between 3 and 5 years of age scheduled for elective surgery will be prospectively enrolled at the Department of Pediatric Surgery, University Hospital of Messina, Italy. Inclusion criteria are the need for elective surgery, in the morning time. Exclusion criteria are children with cerebral malformations and/or injuries, or surgery in the afternoon or at night to eliminate conditions that could affect melatonin production. Children will be also excluded in cases of withdrawal of informed consent, insufficient blood samples, and hemolysis of the blood sample, as hemolysis interferes with the biochemical determination of the OS biomarkers.

Infants matching the clinical criteria for inclusion in the study will then be randomized to be premedicated with oral melatonin (Mel group) or 5% dextrose (Control group)

Permuted, block randomization will be performed by a biostatistics using computerized sequences, and group assignments will be provided in concealed opaque envelopes. Parents of participants will be informed of their infant's group allocation at discharge.

Interventions

- *Mel group:* Melatonin (Dicoson, Dicofarm, Italy, 5 drops = 1 mg) will be administered orally.

The product is listed in the Register of Dietary Supplements on the website of the Ministry of Health (<http://www.ministerosalute.it/alimenti/dietetica>) and is classified with the following code: 943314283. This product is subject to the European Directive on Foodstuffs according to DL n. 169 of May 21, 2004, and not to the European Directive on Medicines 2001/20/EC transposed at the Italian level with D.L. n. 211 of June 24, 2003. Melatonin administration has a good safety profile, with no known adverse effects. Approximately 1 hour before induction of anesthesia, patients will receive oral melatonin or placebo. Mel treated children received a single dose of oral melatonin 0.5 mg/kg (for a max 10 mg). Melatonin (Dicoson, Dicofarm, Italy) will be prepared by a dedicated resident in a fixed volume of 5 mL by adding water to a syringe without a needle.

- *Control group:* Approximately 1 hour before induction of anesthesia, patients will receive 5 mL of 5% dextrose (placebo), used to simulate the sweet taste of the melatonin formulation.

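### The T0/T1/T2 tests name no treatment arm and no test is designated as the test of melatonin, so a time effect could be read as a treatment effect

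*Combined protocol and SAP*

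**What the plan says.** The Introduction states a causal hypothesis: "we test the hypothesis that melatonin, administered as premedication before induction of anesthesia, reduces OS and postoperative pain". Fifteen children are randomised to oral melatonin or dextrose, given about one hour before induction (2.1 and the Interventions text).

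Section 2.6 then lists two families of tests.

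- Over time: "Differences between T0, T1, and T2 will be analyzed by repeated measures ANOVA", with Tukey's procedure, for melatonin, 4-HNE and the two microRNAs. SIRT1 is handled differently: "while by Friedman test followed by" Dunn's test.
- Between arms: "At each experimental time point, comparisons between the Control and Mel treated children will be performed using" an unpaired t-test or a Mann-Whitney test.

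The decision rule covers everything alike: "All data with P < 0.05 will be considered statistically significant". No test is singled out as the test of the hypothesis. No arm-by-time term, adjustment for T0 or between-arm comparison of change from T0 is described.

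**The concern.** The time tests ask whether a marker differs between T0, T1 and T2. They do not ask whether it differs because of melatonin. T0 is taken the day before surgery, T1 is "T1 (after anesthesia, immediately before surgery", and T2 is one hour after surgery and awakening. All children pass through the same events. The Introduction gives a reason to expect oxidative stress to move without any treatment effect: "Pain has been shown to be associated with oxidative stress (OS) in response to tissue injury, inflammation, and cytokine production".

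Two readings of 2.6 are possible, and neither time test isolates melatonin. Run on all children, the test detects the perioperative course. Run within each arm, it invites the conclusion that melatonin worked because one arm changed significantly and the other did not. With seven or eight children per arm, that pattern arises easily by chance. Since the plan gives all P values equal standing, nothing in it prevents such a result from being reported as the main finding.

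**Working it through.** **Plan's own figure.** There is none to reproduce. The total of 15 (2.1) comes without an effect size, SD, power or allocation ratio.

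**Inputs from the document.** N = 15; three sampling times; significance at P < 0.05; anaesthesia and surgery for all between T0 and T2.

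**Assumptions.** Eight Mel and seven Control; two-sided tests; normal values with SD 1 at each time; equal correlation of 0.3, 0.5 or 0.7 between times; a rise common to both arms of 0.5, 1.0 or 1.5 SD by T2, half of it present at T1. The document gives none of these. Each setting used 20,000 simulated trials.

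**Tests compared.** With n children and k = 3 times:

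- Time-only ANOVA: F = [SS(time)/(k − 1)] / [SS(residual)/((n − 1)(k − 1))].
- Arm-by-time: F = [SS(arm × time)/(k − 1)] / [SS(residual within arms)/((N − 2)(k − 1))], where N = 15.
- Planned T2 comparison: unpaired t on 13 degrees of freedom.
- T2 adjusted for T0: regression of T2 on arm and T0, 12 degrees of freedom.

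**Step 1: no melatonin effect.** Each cell gives results for a common rise of 0.5 / 1.0 / 1.5 SD.

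| Correlation | Time ANOVA significant, Mel arm | Time ANOVA significant, pooled | Exactly one arm significant |
|---|---|---|---|
| 0.3 | 15 / 47 / 82% | 27 / 80 / 99% | 24 / 49 / 33% |
| 0.5 | 19 / 61 / 93% | 36 / 92 / 99.9% | 29 / 49 / 17% |
| 0.7 | 29 / 84 / 99.5% | 55 / 99 / 100% | 40 / 32 / 2% |

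In the same trials the arm-by-time test and the planned T2 t-test each reject in about 5%, whatever the rise. At correlation 0.5, exactly one arm is significant while both the T1 and T2 t-tests are null in about 26 / 44 / 15% of trials. The misleading pattern therefore usually appears when the valid tests show nothing.

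**Step 2: the within-arm test does not track the effect.** At correlation 0.5 and a common rise of 1.0 SD, the Mel-arm ANOVA is significant in 61% of trials with no melatonin effect and in 62% with a 1.5 SD reduction at T2.

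**Step 3: what the between-arm tests can detect.** For a difference of d SD at T2, the t-test has noncentrality d × √(8 × 7/15) = 1.932d. At d = 1 this is 1.932, with exact power 43%. At d = 1.5 it is 2.898, with exact power 76%. Adjusting for T0 reduces the residual SD by about √(1 − ρ²), to 0.954, 0.866 or 0.714 at ρ = 0.3, 0.5 or 0.7. Simulated power for a 1 SD effect at T2 only:

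| Correlation | Planned T2 t-test | T2 adjusted for T0 | Arm-by-time |
|---|---|---|---|
| 0.3 | about 43% | 44% | 34% |
| 0.5 | about 43% | 50% | 45% |
| 0.7 | about 43% | 66% | 67% |

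The adjusted comparison is never materially worse than the planned t-test. The arm-by-time test is worse at low correlation.

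**The case against.** The strongest reply is that the plan already tests melatonin. The Control v Mel comparisons at T1 and T2 are post-treatment comparisons of randomised arms. A shift common to both arms cancels, and each test keeps 5% error. A reader might infer from the time tests that the plan cannot attribute anything to melatonin, or lacks a between-arm comparison. The document does not support that: a difference in level at T1 or T2 can properly be attributed to treatment.

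Three other strong readings also go too far.

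- That surgery certainly moves every marker in both arms. The Introduction makes this plausible for oxidative stress, gives no size, and does not say it of SIRT1, melatonin or the microRNAs.
- That the ANOVA definitely excludes an arm factor. The text names none but does not rule one out; only the Friedman test is certain to have no arm term.
- That an arm-by-time ANOVA is simply the better test. Step 3 shows that this depends on a correlation the document does not give.

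It is also true that 2.6 nowhere says significance in one arm only will be taken as a melatonin effect. The 2% to 50% is the error rate of a conclusion the plan leaves open, not of one it commits to.

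What remains is that no test is designated for the hypothesis, within-arm results have equal standing with between-arm ones, and T0 is collected but not used in the treatment comparison.

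**Conclusion.** The concern holds in a limited form. As written, the T0/T1/T2 tests cannot support a conclusion about melatonin, whether run per arm or pooled, and 2.6 neither says so nor names the test that can. If significance in one arm only were read as an effect, the false-positive rate would be about 2% to 50% under the assumed common rise of 0.5 to 1.5 SD and correlation of 0.3 to 0.7, against about 5% for a between-arm test. The figure is highly sensitive to these assumptions: it peaks at a moderate rise and almost vanishes when the rise is large and the correlation high. The planned between-arm tests are valid, so the defect is one of designation and unused baseline information. It should be corrected, but it does not invalidate the trial.

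**What to change.** In 2.6:

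1. For 4-HNE, name the between-arm comparison of T2 adjusted for T0, and likewise T1 adjusted for T0, as the test of melatonin. Give arm-by-time as a supporting analysis.
2. For SIRT1, compare the changes from T0 between arms by Mann-Whitney, or use a rank-based comparison adjusted for T0.
3. State whether the T0/T1/T2 tests run per arm or pooled, and label them as description of the perioperative course.
4. State that no treatment conclusion will be drawn from significance in one arm and not the other.
5. Treat the microRNA results as descriptive only, since 2.5 gives three samples at each time point.

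The cost is wording, one extra model and one degree of freedom for T0; no new samples or children are needed. The sponsor should confirm that the software named in 2.6 fits the adjusted model. Within-arm P values lose their standing as evidence for melatonin. The gain in power depends on the unknown T0–T2 correlation and is negligible if that is low.

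### Run per arm, Dunn's test for SIRT1 cannot declare a contrast between neighbouring ranks when all 7 or 8 children share one order over T0, T1 and T2; exact paired Wilcoxon tests after Friedman can

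*Combined protocol and SAP*

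**What the plan says.** Section 2.6 sets the within-child analysis over T0, T1 and T2. Melatonin, 4-HNE and the two microRNAs get repeated measures ANOVA with Tukey's test; SIRT1 gets "Friedman test followed by Dunn's test in the case of SIRT1 levels". The threshold is "All data with P < 0.05 will be considered statistically significant", and the software is named: "GraphPad Prism 6.0 (GraphPad Software, Inc., San Diego, CA, USA) will be used for statistical analysis".

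Section 2.1 gives the size: "Fifteen Children between 3 and 5 years of age scheduled for elective surgery will be prospectively enrolled". They are randomized to two groups ("Permuted, block randomization will be performed by a biostatistics using computerized sequences"), with no allocation ratio or arm sizes. Children can be dropped for "insufficient blood samples, and hemolysis of the blood sample".

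The plan does not say whether the Friedman test is run within each arm or on all 15 children, or which multiplicity adjustment goes with Dunn's test. It gives no power calculation. The arms are compared separately: "comparisons between the Control and Mel treated children will be performed using Student's t-test for unpaired data or Mann-Whitney U test".

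**The concern.** SIRT1 is the direct marker of the sirtuin pathway named in the hypothesis at the end of the Introduction, and the plan intends to say between which time points it changes. Dunn's test after Friedman ranks each child's three values and sums the ranks. When every child has the same order, the sums are n, 2n and 3n, so two neighbouring sums differ by exactly n whether the underlying change is small or very large. In an arm of 7 or 8, n is smaller than the difference that the test requires.

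What would be lost is where the change happened. Under a steady trend, neither T0-T1 nor T1-T2 can be declared. Under a rise at T1 with partial return at T2, it is T0-T2, the change from baseline to after surgery, together with T1-T2. Within such patterns the power for these contrasts falls as the true effect grows.

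**Working it through.** The plan gives no power or effect size for SIRT1, so there is no figure to reproduce.

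**Inputs.** From the plan: 15 children, two arms, k = 3 time points, threshold 0.05. Assumed: per-arm analysis, a 7/8 split, two-sided tests, Bonferroni over 3 pairs, no tied values.

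**Dunn's test.** z = |Ri − Rj| / √(n·k·(k+1)/6), which for k = 3 is |Ri − Rj| / √(2n). The two-sided critical z at 0.05/3 is 2.394.

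| All children in one order | n = 7 | n = 8 |
|---|---|---|
| Rank sums | 7, 14, 21 | 8, 16, 24 |
| SE = √(2n) | 3.742 | 4.000 |
| Critical difference = 2.394 × SE | 8.96 | 9.58 |
| Neighbouring difference = n | 7 | 8 |
| z | 1.871 | 2.000 |
| Raw P | 0.0614 | 0.0455 |
| Adjusted P (×3) | 0.184 | 0.137 |
| Extreme pair (difference 2n), adjusted P | 0.0005 | 0.0002 |
| Friedman Q = 2n, chi-square P | 14, 0.0009 | 16, 0.0003 |
| Exact Wilcoxon on the neighbouring pair, P = 2/2^n | 0.016 | 0.008 |

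**Smallest n.** A unanimous neighbouring contrast has z = n/√(2n) = √(n/2). It needs n ≥ 2 × 2.394² = 11.46, that is 12.

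**Sensitivity of the ceiling.**
- If every child moves the same way and the third value lies between the pair in one child, the difference is n + 1: adjusted P = 0.098 (n=7) or 0.073 (n=8), still not declared. In two children it is n + 2: 0.0485 or 0.037, declared.
- With a factor of 2 in place of 3, the unanimous values are 0.123 and 0.091. Unadjusted, n=7 still fails (0.061) and n=8 passes (0.0455).
- With all 15 pooled, z = 15/√30 = 2.739 and adjusted P = 0.0185: declared.

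**A step that holds.** If T0 is extreme in every child and the T1/T2 order is a coin flip, T0-T1 is declared when T2 lies on the T0 side of T1 in at least 2 children. The probability is 1 − (1+7)/128 = 0.94 (n=7) or 1 − (1+8)/256 = 0.96 (n=8).

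**Power.** 20,000 simulated data sets per setting, normal data, within-child correlation 0.7, changes in SD units (all assumed). Friedman uses its chi-square P value here.

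| Pattern, contrast | n | Dunn | Wilcoxon after Friedman |
|---|---|---|---|
| Equal steps 0.8, T0-T1 | 7 | 11% | 58% |
| Equal steps 1.0, T0-T1 | 7 | 8% | 78% |
| Equal steps 1.5, T0-T1 | 7 | 1% | 98% |
| Step of 1.5 that holds, T0-T1 | 7 | 82% | 95% |
| Rise 1.5, half return, T0-T1 | 7 | 93% | 93% |
| Rise 1.5, half return, T0-T2 | 7 | 11% | 53% |
| Rise 3, half return, T0-T2 | 7 | 1% | 98% |
| Equal steps 0.8, T0-T1 | 15 pooled | 40% | 95% |

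Under the null, the family error of Wilcoxon after Friedman is about 4% at n=7 and n=8.

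**Exact or chi-square Friedman.** At n=7 the value Q = 6 has chi-square P = exp(−3) = 0.0498 but exact P = 0.051, so only the exact version strictly holds 5%. Repeating the n=7 simulation with the exact P, the held-step figure becomes 94%. For the extreme pair after a rise of 1.5 with half return, it is 88%, against 93% for Dunn's test without a Friedman gate and 88% for Dunn's test behind the same exact gate.

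**The case against.** A reader might infer that Dunn's test cannot detect any step in which every child moves the same way, so that large and consistent SIRT1 changes would be reported as non-significant. The documents do not support that. The third time point must also keep its place in all, or all but one, of the children. T1 and T2 both follow a single premedication dose (sections 2.1 and 2.4), so a step that holds is at least as plausible as a steady trend, and it is usually declared. Falling power with growing effect belongs to shared-order patterns, not to the test in general. Even in the blocked pattern the Friedman test and the extreme pair are significant, so a SIRT1 change is reported. Section 2.6 nowhere says that a non-significant contrast will be read as no change.

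The absolute ceiling also depends on a per-arm analysis, a 7/8 split and a factor of 3, none of which is stated. The melatonin effect itself is tested between arms, where Dunn's test plays no part. Friedman followed by Dunn is a standard pairing, and this is a pilot.

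All of this stands, and it limits the point to which time contrasts can be declared. It does not remove it. The plan sets out these contrasts in their own right, the power loss persists when the arms are pooled, and behind the same Friedman gate the paired test matched or beat Dunn's, to simulation error, in each pattern above.

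**Conclusion.** The point holds in a limited form. Per arm, with 7 and 8 children and a Bonferroni factor of 3 (all assumed), a SIRT1 contrast between neighbouring ranks cannot reach P < 0.05 when the children share one order, whatever its size. Two of the three contrasts are then out of reach. Outside that pattern the loss is modest, as for a step that holds. Pooling all 15 lifts the ceiling, leaves a substantial loss for equal steps, and would mix treated and control children. The overall SIRT1 finding and the between-arm comparisons are untouched. The power figures rest on the assumed normal model; the ceiling rests only on rank arithmetic. It is worth correcting before analysis because the correction is cheap, not because the trial's main conclusion depends on it.

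**What to change.** In section 2.6, replace Dunn's test for SIRT1. After a Friedman test significant at 0.05 by its exact P value, compare each pair of time points with the exact two-sided paired Wilcoxon signed-rank test at 0.05. With three time points, any two pairwise equalities together imply the overall null, so this is a closed procedure and holds the family error at 5% without further adjustment. Report the median paired change for each pair with its confidence interval, and state that the analysis is per arm.

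The cost is one or two sentences, with the same samples and a standard test. There are two downsides. The exact Wilcoxon test cannot reach 0.05 with fewer than 6 complete children in an arm (2/2^5 = 0.0625 at n=5; 2/2^6 = 0.031 at n=6), which matters because samples can be excluded. At n=7 the exact Friedman gate is also slightly stricter than the chi-square one, which costs a little power for the extreme pair.

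### Section 2.6 calls every P < 0.05 significant and names no lead comparison: about a 24% to 34% chance of at least one false arm difference among the eight post-dose marker tests that bear on the hypothesis

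*Combined protocol and SAP*

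**What the plan says.** The Introduction states a hypothesis test: "we test the hypothesis that melatonin, administered as premedication before induction of anesthesia, reduces OS and postoperative pain". It calls the study a pilot but does not label any analysis exploratory.

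Section 2.6 sets out three groups of tests.

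- **Over time.** T0, T1 and T2 are compared by repeated measures ANOVA with Tukey's test for "melatonin, 4-HNE, miR34 and miR124a plasma levels", and by the Friedman test with Dunn's test "in the case of SIRT1 levels". That makes five markers.
- **Between arms.** "At each experimental time point, comparisons between the Control and Mel treated children will be performed". The choice between a parametric and a rank test is left open.
- **Correlations.** Linear regression and Pearson correlation between variables, with no number given.

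One threshold covers everything: "All data with P < 0.05 will be considered statistically significant". The document names no primary outcome, primary time point or testing order, and no adjustment across markers or across the arm comparisons.

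On timing, Section 2.4 describes the first sample as "T0 (pre-hospitalization, 1 day before surgery". Section 2.1 places dosing later: "Approximately 1 hour before induction of anesthesia, patients will receive oral melatonin or placebo". FLACC scores and paracetamol doses are collected under Section 2.3, but Section 2.6 does not mention them.

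**The concern.** When each of many comparisons may be called significant at 0.05 and none leads, the chance that at least one crosses the line by luck is well above 5%. The hypothesis covers oxidative stress, pain and the sirtuin pathway, so a chance difference on one marker at one time could be presented as support for it. With 15 children, a reader could not tell such a result from a real one.

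The T0 comparisons add a separate problem. Children are randomised and T0 precedes dosing, so any arm difference there is due to chance. The rule would still call it significant.

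**Working it through.** The plan states no family-wise error rate, power or sample-size calculation, so there is no figure of its own to reproduce. The only stated number is the per-test threshold.

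**Inputs from the document**

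- Threshold: 0.05 for each test (2.6). Sidedness is not stated; two-sided is assumed.
- Markers: melatonin, 4-HNE, SIRT1, miR-34 and miR-124a (2.6).
- Time points: T0, T1 and T2 (2.4 and 2.6).
- Children: 15 in total (2.1). The allocation ratio is not stated; 8 v 7 is assumed.
- MicroRNA samples: N=3 at each time point (2.5). Whether this is per arm or in total is not stated.

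**Step 1: count the comparisons**

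- All arm comparisons: 5 markers × 3 times = 15. The sentence on arm comparisons does not list the markers; they are taken from the sentence before it.
- Pre-dose, at T0: 5 × 1 = 5.
- Exposure checks, melatonin at T1 and T2: 1 × 2 = 2. Children given oral melatonin should differ here whether or not it has any benefit.
- Remaining post-dose comparisons: 15 − 5 − 2 = 8 (4-HNE, SIRT1 and two microRNAs, each at T1 and T2).

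**Step 2: chance of at least one false arm difference, if independent**

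Formula: 1 − 0.95^k.

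- One pre-specified comparison: 1 − 0.95 = 5%.
- Eight comparisons: 1 − 0.95^8 = 1 − 0.6634 = 33.7%.
- Four comparisons (4-HNE and SIRT1 only): 1 − 0.95^4 = 1 − 0.8145 = 18.5%.

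**Step 3: allow for correlation**

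The tests use the same children and related markers, so independence is an upper case. The documents give no correlations. Null trials of 8 v 7 children with normal data were simulated, at least 20,000 per setting, with within-child correlation from 0 to 0.8 and between-marker correlation from 0 to 0.5.

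- Eight tests, all t-tests: 32% at within-child 0.5 with independent markers; 24% at within-child 0.8 and between-marker 0.5.
- Eight tests with an exact Mann-Whitney test for SIRT1: 32% with no correlation, down to 23% at 0.8 and 0.5. The exact test is slightly conservative at this size.
- Four tests, all t-tests: 14% at 0.8 and 0.5 (13% with the exact test for SIRT1).

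**Step 4: can the microRNA tests reach significance?**

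At 3 v 3, the smallest two-sided exact Mann-Whitney P is 2 / C(6,3) = 2/20 = 0.10, so that test can never fall below 0.05. A t-test at 3 v 3 still could. If N=3 is the total, an arm comparison is barely possible. The four-test figures apply where the microRNA tests cannot reach significance.

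**Step 5: direction**

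Counting only errors in one given direction, each test contributes 0.025: 1 − 0.975^8 = 1 − 0.8167 = 18.3%, about half of 33.7%.

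**The case against.** Four objections deserve an answer.

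**The study is a pilot.** This lessens the consequences of a false claim. It does not remove the problem, because the Introduction says a hypothesis is tested and Section 2.6 gives an unqualified significance rule.

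**Multiplicity is already handled.** This is true in part. Tukey's and Dunn's tests are multiple-comparison procedures, so it would be wrong to infer that the plan has no control at all. They follow the T0/T1/T2 analyses only, and they cover neither the arm comparisons nor the correlations.

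**The size is easily exaggerated.** This stands. A reader might infer that a null trial would find an effect about half the time, since 1 − 0.95^15 = 53.7%. That figure assumes independence and counts five pre-dose tests and two exposure checks, none of which can yield a false treatment effect. A reader might also add ten time analyses (five markers in each of two arms) and reach 1 − 0.95^25 = 72.3%. The documents do not support that either. The plan does not say that the time analyses are run by arm, and markers may shift across anaesthesia and surgery without any treatment effect, so a significant time change is not a false positive for melatonin.

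**A difference in the wrong direction is not support.** This also stands for oxidative stress and pain, and it halves the figure roughly. The hypothesis sentence gives no direction for SIRT1 or the microRNAs.

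**Conclusion.** The point holds in limited form. Section 2.6 lets any of 15 arm comparisons, and an unstated number of correlations, be called significant at 0.05, with no lead comparison and no control between arms.

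For the eight post-dose comparisons that bear on the hypothesis, the chance of at least one false arm difference is about 34% if independent and about 24% to 32% under the assumed correlations, against 5% for one pre-specified comparison. It is about 14% to 19% if the microRNA tests cannot reach significance. About half of these errors would be in the hypothesised direction.

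The absence of a lead comparison is plain from the text. The size is less certain: it rests on assumed correlations, an assumed 8 v 7 split, two-sided tests and an unclear microRNA sample size. Correlations would add further chances of a false claim, but their number cannot be fixed from the text, so they are not in these figures. Nor are FLACC and paracetamol doses, which Section 2.6 does not name.

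**What to change.** Before unblinding, replace the significance sentence in Section 2.6 with a statement that does the following.

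1. **Name one primary arm comparison**, by marker, time point and test, at two-sided 0.05. 4-HNE at T2 is the natural candidate: Section 2.4 uses it to evaluate oxidative stress, and T2 is the only sample taken after surgery. The investigators may name another.
2. **Define pain if it is to be claimed as well.** Section 2.3 gives no FLACC summary or assessment time for analysis. Choose one summary, one time point and one test, then either test it in fixed sequence with the primary comparison or split the 0.05 between the two.
3. **Label all other arm comparisons and the correlations exploratory.** Report them as estimates with 95% confidence intervals and do not declare them significant.
4. **Treat post-dose melatonin as an exposure check**, and do not test the arms against each other at T0.

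The cost is one paragraph, with no extra children, samples or assays. Some secondary results lose the label of significance. Under a fixed sequence the second outcome is formally tested only if the first succeeds, which matters here because the hypothesis names both oxidative stress and pain. Splitting alpha avoids that, at the price of a stricter threshold for each.
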